12.3.4.2. Time to 50% reduction in pRBC transfusion

Time to 50% reduction in pRBC transfusion (in weeks) is measured from the day of first study drug to the first day of response of 50% reduction of pRBC transfusion or a censor date. See [Section 12.3.3.1](#) for the detail of definition of the response.

- for those who have a response, time to 50% reduction in pRBC transfusion will be calculated as duration = first day of response - day of first study drug + 1
- for those who do not have a response, time to 50% reduction in pRBC transfusion will be calculated as duration = date of the end of study or treatment discontinuation due to AE/SAE or death, whichever comes earlier - day of first study drug + 1.

Median time to 50% reduction in pRBC transfusion will be estimated using Kaplan-Meier (K-M) method and its associated 2-sided 95% CIs for each treatment group will be calculated using the method of Brookmeyer and Crowley. The estimated survival probability and its associated 2-sided 95% CIs for each treatment group up to 52 weeks by every 4-weeks will be estimated by Kaplan-Meier product limit method. Kaplan-Meier curves will also be presented by treatment group.

Sample SAS codes are presented as below:

```
PROC LIFETEST DATA= PLOTS=SURVIVAL;  
    TIME value*censor (1);
```

```
STRATA treatment;
```

```
SURVIVAL OUT=xx;
```

```
RUN;
```

Treatment comparison will be performed using the stratified log-rank test stratified by randomization factors.

Sample SAS codes are presented as below:

```
PROC LIFETEST DATA=;  
    TIME value*censor (1);  
    STRATA <stratum_var>/GROUP=treatment;
```

```
RUN;
```

Time to 50% reduction in pRBC transfusion will be compared between treatment groups using the Cox regression model, controlling for baseline hemoglobin and the stratification factors. Two-sided 95% CI of the hazard ratio will be presented for the treatment difference. Sample SAS codes are presented as below:

```
PROC PHREG DATA=;  
    MODEL value*censor (1)= treatment base_hb <stratum_var>;
```

```
RUN;
```

Model checking: The proportional hazards assumption will be checked graphically using a log-cumulative hazard plot against log-survival time. This plot will give approximately parallel lines if the proportional hazards assumption between treatment arms subgroups holds. If the proportional hazard assumption is violated, then stratified Cox Model (with stratification-factors in STRATA statement) will be used instead.

12.3.4.3. Maximum Duration of transfusion independence (TI)

Duration of TI (in weeks) is measured from the first day of the TI response anytime during the study to the date of the first RBC transfusion after this period or a censor date. See [Section 12.3.3.1](#) for the detail of definition of TI response. If a patient has more than one at least 56-day period with transfusion free, i.e., more than one TI response period, then the one with the maximum duration will be used for analysis.

- for those who receive a subsequent RBC transfusion, the duration of TI will not be censored and will be calculated as duration = last day of TI response - first day of TI response +1 where the last day of response is defined as 1 day before the first subsequent RBC transfusion which is given at 56 days or more after the response starts.
- for those who do not receive a subsequent RBC transfusion, the end day of the TI response will be censored as in [Section 12.3.3.1](#) and duration of the TI response will be calculated as duration = date of the end of study or treatment discontinuation due to AE/SAE or death, whichever comes earlier - first day of TI response + 1.

A Frequency summary with regard to patients who had a transfusion after the TI response with the maximum duration of the TI response, patients who maintained transfusion independence until the censored date will be provided by treatment group.

Median maximum duration of TI will be estimated using Kaplan-Meier (K-M) method and its associated 2-sided 95% CIs for each treatment group will be calculated using the method of Brookmeyer and Crowley. The estimated survival probability and its associated 2-sided 95% CIs for each treatment group up to 52 weeks by every 4-weeks will be estimated by Kaplan-Meier product limit method. Kaplan-Meier curves will also be presented by treatment group.

Sample SAS codes are presented as below, the 'input dataset' will consist of TI responders only:

```
PROC LIFETEST DATA= PLOTS=SURVIVAL;  
    TIME value*censor (1);  
STRATA treatment;
```

SURVIVAL OUT=xx;

RUN;

Treatment comparison will be performed using the stratified log-rank test stratified by randomization factors.

Sample SAS codes are presented as below:

```
PROC LIFETEST DATA=;  
    TIME value*censor (1);  
    STRATA <stratum_var>/GROUP=treatment;
```

RUN;

Maximum Duration of TI will be compared between treatment groups using the Cox regression model, controlling for baseline hemoglobin and the stratification factors. Two-sided 95% CI of the hazard ratio will be presented for the treatment difference. Sample SAS codes are presented as below:

```
PROC PHREG DATA=;  
    MODEL value*censor (1)= treatment base_hb <stratum_var>;
```

RUN;

Model checking: The proportional hazards assumption will be checked graphically using a log-cumulative hazard plot against log-survival time. This plot will give approximately parallel lines if the proportional hazards assumption between treatment arms subgroups holds. If the proportional hazard assumption is violated, then stratified Cox Model (with stratification-factors in STRATA statement) will be used instead.

Summary statistics for duration of response (in weeks) as well as a frequency summary of duration of Response by different time points (e.g. ≥ 8 weeks, ≥ 16 weeks, etc.) will also be provided.

12.3.4.4. Proportion of patients who achieve a mean Hb increase of ≥ 1.0 g/dL and ≥ 1.5 g/dL (averaged over 8 weeks in those that achieved TI) compared to pre-transfusion Hb at baseline)

Moving average (MA) of change from baseline in Hb will be calculated for any 8-week window (e.g., Days 1 to 56, Days 2 to 57, Days 3 to 58, etc.), starting at Week 1 day 1 post-dose.

Baseline Hb value is defined as the mean of screening central laboratory Hb value and week 1 Day 1 Hb value prior to treatment. For each post-baseline 8-week window, a minimum of 3 evaluable Hb assessments is required for 28-week analysis (only one assessments every 4 weeks after Week 31.); otherwise, the mean is set to missing in the corresponding window. A patient is considered a responder of this endpoint during the treatment period if

- Transfusion independent for ≥ 56 days consecutively;
- The moving averages of change from baseline in Hb is ≥ 1.0 g/dL (or ≥ 1.5 g/dL) during the treatment period.

The following summaries will be provided based on FAS:

- Analysis of average change from baseline in Hb by every 8-week period (e.g., 56 consecutive days)
- Number and percentage of TI responder and non-responder

Baseline Hb, absolute Hb value and change from baseline at each scheduled post-baseline visit

The following summaries will be provided for TI responders in FAS:

- The proportion of patients who achieve a mean Hb increase of ≥ 1.0 g/dL averaged over any 8 weeks
- The proportion of patients who achieve a mean Hb increase of ≥ 1.5 g/dL averaged over any 8 weeks

The denominator for the proportions is FAS population.

Similar methods will be used as in [Section 12.3.1.1](#).

Mean (\pm SE) Hb (g/dL) from Baseline to Week 28 and to Week 52 will be plotted by treatment groups.

12.3.4.5. Impact of baseline endogenous erythropoietin levels on roxadustat treatment response and dose requirement

TI response rate (RBC TI at least ≥ 8 weeks) will be analyzed by baseline endogenous EPO level (< 200 mIU/mL **OR** > 200 mIU/mL and ≤ 400 mIU/mL) using the methods described in [Section 12.3.1](#). A summary table will be provided. See [Section 12.3.3.1](#) for the detail of definition of TI response.

Average weekly exposure data will be analyzed by baseline endogenous EPO level and treatment group.

The average weekly dose will be analyzed by baseline endogenous EPO level (< 200 mIU/mL **OR** > 200 mIU/mL and ≤ 400 mIU/mL) and treatment group.

In order to compare patients with baseline endogenous EPO level < 200 mIU/mL to patients with baseline endogenous EPO level > 200 mIU/mL and ≤ 400 mIU/mL), the ANCOVA with baseline Hb value as covariate and baseline endogenous EPO level as class category.

RBC TI response analysis as primary efficacy endpoint will be repeated for each level of baseline EPO: ≤ 100 , ≤ 200 , ≤ 300 and, ≤ 400 mIU/mL.

Proportion of patients who achieve a mean Hb increase of ≥ 1.0 g/dL and ≥ 1.5 g/dL (averaged over 8 weeks in those that achieved TI) compared to pre-transfusion Hb at baseline will be summarized for each level of baseline EPO: < 200 mIU/mL **OR** > 200 mIU/mL and ≤ 400 mIU/mL.

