12.3.4. Analysis of Exploratory Efficacy Endpoints

P values generated from treatment comparison for exploratory endpoints are exploratory, no multiplicity adjustment will be needed. Nominal p-values are used primarily as measures of strength of association rather than formal criteria to claim statistical significance. The nominal p-values will also be explained in table footnotes. All analysis will be performed using the FAS.

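### Maximum duration of TI is compared between arms in TI responders only, so its log-rank p-value and hazard ratio are not randomized comparisons and can be biased in either direction

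*SAP*

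**What the plan says.** SAP 12.3.4.3 defines duration only for patients with a transfusion-free period of at least 56 days: "Duration of TI (in weeks) is measured from the first day of the TI response anytime during the study". It ends at the next RBC transfusion or at a censoring date. Where a patient has several such periods, "the one with the maximum duration will be used for analysis".

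The sentence that introduces the Kaplan-Meier code states that the input dataset "will consist of TI responders only". Two between-arm comparisons follow:

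- "Treatment comparison will be performed using the stratified log-rank test stratified by randomization factors".
- "Maximum Duration of TI will be compared between treatment groups using the Cox regression model, controlling for baseline hemoglobin and the stratification factors". A 95% CI for the hazard ratio is presented as the measure of treatment difference.

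Both code samples use the same dataset placeholder as the Kaplan-Meier code, and a non-responder has no duration to contribute. The two preceding endpoints (SAP 12.3.4.1 and 12.3.4.2) differ here: they keep non-responders and censor them.

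The opening of SAP 12.3.4 says of the exploratory endpoints: "All analysis will be performed using the FAS". It also says that their p-values are nominal and need no multiplicity adjustment.

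**The concern.** Whether a patient enters this analysis depends on treatment. Placebo responders are the few patients who would have gone 56 days without a transfusion anyway. Roxadustat responders are that kind of patient plus those whom the drug converted. The two groups can differ in prognosis even if the drug helps everyone. Adjusting for baseline hemoglobin and the stratification factors does not restore comparability, because these variables need not capture what separates a natural responder from a converted one.

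The risk is a hazard ratio and CI that are read as the drug's effect on durability of response when they mix that effect with selection. The bias can work against the drug or flatter it.

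**Working it through.** **Inputs.** SAP 12.3.4.3 states no planning figure of its own. SAP 3.2 gives 56% and 13% for 28-week TI with 120 patients at 3:2. SAP 17 gives 140 enrolled, about 84:56 at 3:2. The SAP 3.2 power statement (at least 90%, two-sided Fisher's exact test) holds: exact enumeration at 72:48 gives 99.9%.

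**Responder counts if the 28-week rates applied.**

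- Roxadustat: 0.56 × 84 = 47.0. Placebo: 0.13 × 56 = 7.3.
- If the drug only adds responders, (56 − 13)/56 = 43/56 = 77% of roxadustat responders have no counterpart among placebo responders.
- Across 8 strata, 7.28/8 = 0.9 placebo responders per stratum.

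The endpoint uses TI at any time during the study, so actual counts may be higher.

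**Direction of the hazard ratio.** The documents give no duration distribution, so these are assumptions. Placebo responders have runs of 8 + Exp(mean 24) weeks, with true median 8 + 24 × ln 2 = 24.6 weeks. The same patients gain 3 weeks on drug. A further 43% of patients become responders on drug, with runs of 8 + Exp(mean m) weeks. Runs are censored at 44 weeks. Every patient therefore does better on drug. The estimate is the unstratified one-step log-rank hazard ratio, exp[(O − E)/V] for roxadustat, where a value above 1 means faster loss of TI on drug.

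| m (weeks) | Average HR at trial size (84:56) | Cox HR, very large sample |
|---|---|---|
| 12 | 1.36 | about 1.6 |
| 18 | 1.07 | 1.1 to 1.2 |
| 24 | 0.82 | just under 1 |
| 36 | 0.54 | about 0.7 |

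The trial-size averages lie below the large-sample values, which fits an estimate resting on only about 7 placebo responders. At m = 12 the HR exceeds 1 in about 83% of simulated trials, and about 14% are nominally significant against the drug.

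**A second set of assumptions.** Exponential time beyond day 56, censoring at 364 days, and a drug that multiplies the run by 1.25 in those who would respond anyway (their own HR is 0.70 to 0.75). Large-sample responder-only HR, by mean excess in newly converted responders:

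| Mean excess, placebo-type responders | 40 d | 80 d | 120 d | 200 d | 300 d |
|---|---|---|---|---|---|
| 200 days | 2.10 | 1.65 | 1.36 | 0.90 | 0.64 |
| 100 days | 1.55 | 1.12 | 0.81 | 0.57 | 0.41 |

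In the same scenarios, a rank test on all patients with non-responders scored 0 favours the drug with at least 99.7% power. If the drug simply stretches one lognormal distribution of run lengths, the responder-only HR is 0.47 to 0.50 and there is no reversal.

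**Precision.** With 47 + 7 = 54 responders, of whom 13.4% are on placebo, the Schoenfeld formula gives 41% power for a true HR of 0.5 if every responder has an event, and 27% if 60% do.

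**The case against.** The strongest reply is that little rests on this analysis. The endpoint is exploratory, its p-values are nominal, and it appears neither in the gatekeeping list (SAP 12.3.2, Table 4) nor in the Week 28 output (SAP 19.9). The FAS is already used for comparisons that reflect duration: cumulative patient-exposure-weeks (PEW) of TI with non-responders at zero (SAP 12.3.3.3, test 5), TI of at least 140 days (SAP 12.3.3.5, test 7), and TI rates at 8, 12, 16 and 20 weeks (SAP 12.3.1.1). All of this stands, and it limits the impact. It does not make the hazard ratio a randomized comparison: calling a p-value nominal deals with multiplicity, not with selection.

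Two stronger readings are tempting, and the documents do not support them.

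- A reader might infer that the hazard ratio can take either sign whatever the true effect. It cannot. Restricting to runs of at least 56 days does not itself change the hazard after day 56, so if the drug's hazard is lower at every later time the HR stays below 1. Reversal needs newly converted responders to have clearly shorter runs than placebo responders.
- A reader might infer that a responder-only dataset contradicts the FAS statement in SAP 12.3.4. Responders can be a subset of the FAS, and SAP 12.3.4.4 describes its own subset that way. The wording is unclear, not contradictory.

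**Conclusion.** The concern holds in a limited form. The log-rank p-value and Cox hazard ratio in SAP 12.3.4.3 condition on a post-randomization outcome that the sponsor expects to differ widely between arms (56% vs 13%). They should not be presented as the treatment difference.

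The size and sign of the bias cannot be determined from the documents. In scenarios where every patient benefits, the responder-only HR ran from 0.41 to 2.10. That range rests on assumed durations and on unstratified models without baseline hemoglobin. The counts of 47 and 7 borrow the 28-week rates for an endpoint measured over the whole study.

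No confirmatory claim depends on this analysis. The change is still worth making, because it is cheap and removes an estimate that is easily misread.

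**What to change.** In SAP 12.3.4.3:

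1. Keep the Kaplan-Meier curves, medians and frequency summaries by arm as description, and name the set as TI responders within the FAS. That also settles the wording against SAP 12.3.4.
2. Delete the stratified log-rank p-value and the Cox hazard ratio with its CI.
3. For between-arm inference on duration, refer to PEW of TI (test 5) and TI of at least 140 days (test 7).
4. If a comparison of the longest interval is still wanted, run it in all FAS patients with non-responders at 0, using the stratified rank method of SAP 12.3.3.3. State that runs censored at study end, discontinuation for an adverse event, or death are counted at their observed length. This is a limitation, since such runs are treated as complete.

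The cost is SAP wording. No new data are needed, and step 4 reuses planned code. The downside is that one exploratory hazard ratio is no longer reported.

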### 3.1.1 Screening Period

All screening procedures are to be completed within 28 days prior to Day 1 of Treatment, except for documentation of the following which can be obtained from patient medical records:

1. Lower risk MDS (IPSS-R very low risk, lower risk, or intermediate risk) must be documented prior to Day 1 of Treatment. There is no minimum time from diagnosis to registration/randomization except to allow for proper IPSS-R classification to be made, and to show transfusion dependence for patients in both portions of the study.
2. Results from bone marrow examination and cytogenetic analysis performed within 16 weeks prior to Day 1 of treatment can be used. The required bone marrow slides and report must be available for a centralized review at any time throughout the study.

3. Patients are deemed to have low RBC transfusion burden (LTB) if they received 1 to 4 pRBC documented transfusion within 8 weeks prior to registration/randomization. Patients with 1 pRBC/8-weeks must have a documented history of requiring 1pRBC/ 8-weeks in 2 consecutive periods of 8 weeks in the 16 weeks preceding registration/randomization. Pre-transfusion and post-transfusion Hb levels within 8 weeks prior to Day 1 of treatment will also be recorded. The percentage of patients requiring 1 pRBC transfusion at baseline will be capped at 30% for the DB portion of the study. For OL patients only, the requirement to demonstrate transfusion dependence can also be met by a PI starting this particular patient on pRBC transfusion during the screening period

All patients must meet all inclusion and have none of the exclusion criteria to be eligible to receive study medication.

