### **8.3.2 General Considerations**

Descriptive summaries will be presented for study parameters including baseline characteristics, safety, and efficacy. Continuous variables will be reported in mean, standard deviation or standard error, median, minimum, and maximum.

Categorical variables will be reported by the frequency and percentage of patients within each outcome category.

Analyses of the efficacy data will be based on the FAS Population.

Baseline Hb value for efficacy analysis is defined as the mean of Screening central laboratory Hb value and Day 1 Hb value.

Safety data will be summarized descriptively based on the Safety Population.

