

1. Eligibility review: pre-transfusion Hb measurements will be obtained via review of source document, must be obtained within 72-hours prior to transfusion; baseline Hb level will be obtained 3 to 10 days prior to registration/randomization; GFR will be done prior to registration/randomization (see [Appendix L](#))
2. Serum erythropoietin level must be  $\leq 400$  mIU/mL at screening; during the last month of treatment a serum EPO level will be drawn just prior to the next study drug dosing; patients should be told to not take their study drug until after the study visit on that day.
3. PK: see [Appendix J](#). Levels at 1-3 and 3-5 hours after dosing at clinic on Day 1 (Week 1) as well as 4-6 hours at Week 5 and 8-10 hours at Week 21 after administration at the clinic. Two samples will be obtained 0-2 hours before dosing and 2-3 hours after dosing at Week 25; vital signs will also be taken prior to the time of the PK draw
4. ECG: no clinically significant findings per PI review at screen period
5. Patients will need to have the results from the bone marrow exam and cytogenetic analysis performed for the IPSS-R criteria. Report and slides must be available for centralized review. Bone marrow exam will be done within 4 weeks of end of treatment on all patients

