4.2.3. Exploratory Endpoints

The exploratory efficacy endpoints include:

- Maximum Duration of TI
- Proportion of patients who achieve a mean Hb increase of ≥ 1.0 g/dL and ≥ 1.5 g/dL (averaged over any 8 weeks in those achieved TI) compared to pre-transfusion Hb at baseline
- Impact of baseline endogenous erythropoietin levels on roxadustat treatment response and dose requirement
- Effect on hepcidin and iron indices metabolism (e.g., serum iron, ferritin, TIBC, TSAT, and UIBC)
- Effect on cholesterol and lipid parameters

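### The exploratory Hb-response endpoint (SAP 12.3.4.4) can misclassify responders: the Hb-rise window need not be transfusion-free, and the calculated baseline is not the one the endpoint names.

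*SAP*

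**What the plan says.** **Endpoint name.** SAP 4.2.3 describes the proportion with a mean Hb increase of at least 1.0 and 1.5 g/dL, "averaged over any 8 weeks in those achieved TI) compared to pre-transfusion Hb at baseline". Protocol 2.8.3, the protocol synopsis, the heading of SAP 12.3.4.4 and SAP 12.3.4.5 name the same comparator.

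**Calculation.** SAP 12.3.4.4 states: "Baseline Hb value is defined as the mean of screening central laboratory Hb value and week 1 Day 1 Hb value prior to treatment". This follows the protocol's general rule in section 8.3.2: "Baseline Hb value for efficacy analysis is defined as the mean of Screening central laboratory Hb value and Day 1 Hb value". Neither sentence sets a condition on time since transfusion. Two screening values are planned and a third is allowed (protocol 4.1), but nothing says which enters the mean.

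**Responder rule.** SAP 12.3.4.4 lists two bullets. One is TI for at least 56 consecutive days. The other begins "The moving averages of change from baseline in Hb is" and sets the threshold at 1.0 (or 1.5) g/dL during the treatment period. Moving averages run over every rolling 8-week window from Day 1. At least 3 Hb values per window are required for the 28-week analysis. The denominator is the FAS.

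**Data available.** Protocol 3.1.1: "Pre-transfusion and post-transfusion Hb levels within 8 weeks prior to Day 1 of treatment will also be recorded". Footnote 1 of Appendix A separates the two quantities. For one, "pre-transfusion Hb measurements will be obtained via review of source document, must be obtained within 72-hours prior to transfusion"; for the other, "baseline Hb level will be obtained 3 to 10 days prior to registration/randomization". SAP section 8 lists pre-transfusion Hb as a baseline characteristic in its own right.

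**The concern.** There are two separate gaps.

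1. **Window.** A patient can meet the TI bullet in one stretch of treatment and the Hb bullet in another that contains transfusions. No rule removes Hb values drawn after a transfusion. Restricting the endpoint to patients who achieved TI limits which patients count, not which windows. The tabulated result could then include Hb rises produced by donor cells.

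2. **Baseline.** Double-blind patients enter having received 1 to 4 units in the previous 8 weeks, and transfusions between the screening visits are expected and recorded (protocol 6.1.2). A screening or Day 1 sample can therefore be post-transfusion. The effective threshold then differs from the one the endpoint name implies, and differs from patient to patient.

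At stake is what the endpoint means: a reader of the results would take it as an Hb rise while transfusion-free, measured from pre-transfusion Hb. The same endpoint is tabulated again by baseline EPO level in SAP 12.3.4.5.

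**Working it through.** The documents give no expected rate or power for this endpoint, so there is no figure to reproduce. They also give no Hb rise per unit, no rate of fading and no SD; those values below are assumptions, labelled as such.

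**A. Does the 3-value minimum keep transfused windows out?** Post-baseline Hb days on the protocol schedule are 8, 15, 22, 29, then every 14 days from 43 to 197. Every 56-day window ending by Day 197 holds at least 4 planned values, so the minimum excludes none of them. From Week 31 visits are four-weekly, so a 56-day window holds about 2 values; no minimum is stated for the 52-week analysis.

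**B. Worked patient for the window rule.** Assumptions: true baseline 8.5 g/dL; 2 units on Day 20 and 2 on Day 48, none later; a true rise of 0.4 g/dL from Day 60; each unit adds e g/dL, fading linearly to zero over D days. The patient is TI from Day 49. Change at day d = true rise + sum over past transfusions of 2e × max(0, 1 − (d − t)/D).

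With e = 0.75 and D = 42:
- Days 22–77, which include the Day 48 transfusion: visits 22, 29, 43, 57, 71 give 1.43, 1.18, 0.68, 1.36, 1.08. Mean = 1.14, a responder at 1.0.
- Best transfusion-free window: visits 57, 71, 85, 99 give 1.36, 1.08, 0.58, 0.40. Mean = 0.85, a non-responder.

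Best window over the assumed grid:

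| e (g/dL per unit) | D (days) | Any window | Transfusion-free only | Classification changes? |
|---|---|---|---|---|
| 0.75 | 42 | 1.14 | 0.85 | yes, at 1.0 |
| 0.75 | 56 | 1.36 | 1.16 | no |
| 1.0 | 42 | 1.50 (1.499) | 1.04 | no |
| 1.0 | 56 | 1.78 | 1.44 | yes, at 1.5 |
| 1.25 | 42 | 1.85 | 1.22 | yes, at 1.5 |
| 1.25 | 56 | 2.20 | 1.73 | no |

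The any-window rule always gives the higher value, and it changes the classification in three of six cases. Even the transfusion-free windows average 0.85 to 1.73 against a true 0.4, because the early part of the run still carries donor cells. Tying the windows together is therefore necessary but not sufficient.

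**C. How often could a baseline sample be post-transfusion?** Treat transfusions as m separate episodes per 56 days (an assumption). The chance that a given sample falls within 14 days after one is m × 14/56 if evenly spaced, or 1 − exp(−m × 14/56) if Poisson:
- m = 1: 25% or 22%
- m = 2: 50% or 39%
- m = 3: 75% or 53%
- m = 4: 100% or 63%

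**D. Size of the baseline shift.** Shift = units × rise per unit × (affected samples / 2). One unit, 1 g/dL per unit, one of two samples affected: 1 × 1 × 1/2 = 0.5 g/dL. The 1.0 threshold becomes 1.5 g/dL above pre-transfusion Hb. At 0.5 g/dL per unit the shift is 0.25.

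**E. Effect on the responder share.** Assume true rises among TI patients are normal with mean 1.2 and SD 0.7. Share at or above 1.0 = 1 − Φ((1.0 + shift − 1.2)/0.7):
- shift 0: 61%
- shift 0.25: 47%
- shift 0.5: 33%

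These figures apply if every patient has that shift; a mixture of patients lies between them.

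**The case against.** **Low stakes.** This stands. P values for exploratory endpoints are nominal (SAP 12.3.4), the endpoint is not in the gatekeeping table (SAP 12.3.2), and the Week 28 efficacy analysis covers only the primary endpoint (SAP 19.9).

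**The SAP follows the protocol.** This also stands. The screening/Day 1 mean is the protocol's efficacy baseline (8.3.2), and protocol 6.3.1.1 reserves central-laboratory Hb for analysis. A reader might infer that the SAP departed from the protocol; it did not. The protocol's general rule conflicts with its own name for this endpoint. The SAP cites Amendment 03 and the protocol available is Amendment 02, so a later protocol repair cannot be excluded, but the SAP still contains both wordings.

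**Direction by arm.** A reader might infer that the window gap favours the arm transfused more. The documents do not support that. TI for 56 days is a precondition, so patients who never reach it cannot qualify however often they are transfused, and an arm with more TI patients has more who could qualify. The net direction is unknown. The baseline mismatch arises before treatment, so randomization balances it on average.

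**Count.** A reader might multiply the planning TI rates by arm size to obtain a number misclassified. That would count every TI patient, including those never transfused again and those with a genuine rise.

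**Opposite directions.** A raised baseline hides responders; a transfused window creates them. The two may partly offset, but neither cancels the other patient by patient.

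**Other outputs.** SAP 12.3.4.4 also reports mean Hb change by 8-week period and by visit, and SAP 12.3.1.1 plans a swimming plot of transfusions and TI periods. These help interpretation but do not correct the responder classification.

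**Purpose.** The documents do not state that this endpoint exists to separate better erythropoiesis from changed transfusion practice, so the point does not rely on it.

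**Conclusion.** Both gaps are in the text. The responder rule lets a TI patient qualify on a transfused 8-week window, and the baseline calculated is not the one the endpoint names. Responders can be misclassified; how many, and with what net effect by arm, cannot be computed from the documents.

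The window gap is the more important because it depends on post-baseline transfusions and so can differ by arm. In the worked patient it adds 0.20 to 0.63 g/dL to the best 8-week mean (1.36 − 1.16 to 1.85 − 1.22), under the assumed units, rise per unit and fading. The baseline gap is non-differential on average but can shift the effective threshold, by about 0.5 g/dL in the 1-unit case at an assumed 1 g/dL per unit.

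A reader might infer that the trial's efficacy conclusion is in doubt. It is not: the primary analysis, the secondary analyses and control of type I error do not use this responder rule.

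**What to change.** In SAP 12.3.4.4:

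1. **Window.** Count a patient as a responder only if the 8-week mean rise of at least 1.0 (or 1.5) g/dL falls wholly within the same transfusion-free run of at least 56 days.
2. **Early values in the run.** State how Hb values soon after the last transfusion are handled, for example by leaving out a stated number of days at the start of the run or by a sensitivity analysis that does so. State a minimum number of Hb values for the 52-week analysis.
3. **One baseline.** Either use the recorded pre-transfusion Hb, state the exception to the central-laboratory rule in protocol 6.3.1.1, and keep the screening/Day 1 mean as fallback or sensitivity analysis; or keep the screening/Day 1 mean and rename the endpoint in SAP 4.2.3, 12.3.4.4 and 12.3.4.5.
4. **Screening value.** Say which of the two or three screening values enters the mean.

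The cost is a few sentences and a program change. On item 3, pre-transfusion values may come from local laboratories and are selected low points, so using them invites some regression to the mean; renaming avoids that but leaves a baseline that may be post-transfusion. Before choosing, confirm what was collected: protocol 3.1.1 and 6.1 record pre-transfusion Hb for the 8 weeks before treatment or randomization, while footnote 11 of Appendix A places that collection 8 weeks after registration/randomization, and the passages need reconciling. Fix the choice before unblinding.
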